**INSTRUCTIONS:**

- Carefully complete the protocol.
- DO NOT open or edit in google docs.
- DO NOT upload PDFs of protocol or consent forms. Use PDFs sparingly.
- Depending on the nature of what you are doing, some sections may not be applicable to your research. If so, please mark as N/A.
- When you write a protocol, keep an electronic copy. You will need to modify this copy when making changes.
- Consider using a different color font for your answers.

## 1.0 Funding

If this study is grant funded, is the money coming directly to CWRU from the study sponsor?

Yes  No  N/A, not grant funded

## 2.0 Objectives

**Directions: Describe the purpose, specific aims or objectives. Be sure to also include the hypothesis being tested.** The purpose of this study is to pilot a culinary nutrition and food literacy intervention entitled Nourish and its corresponding evaluation components to evaluate their feasibility and engage participants in the re-design of the intervention following completion of the Nourish pilot. Specifically, we aim to:

1. Determine whether the Nourish intervention is delivered as intended in terms of time use and objectives delivered.
2. Determine the feasibility of the recruitment, retention, evaluation, and participant engagement methods.
3. Assess participant perspectives on the Nourish intervention so they can be leveraged to re-design the intervention to ensure they are culturally and socially relevant.

## 3.0 Background

**Directions: Describe the relevant prior experience and gaps in current knowledge describing how this study will add to existing knowledge. Include any relevant preliminary data.** Currently, 12.8% of Americans experience food insecurity (1), and food insecurity is associated with elevated perceived stress (2-3). Food literacy is proficiency in food related skills and knowledge, including food preparation and cooking skills, basic nutrition knowledge, and the ability to prevent food waste. Recent research conducted in Australia suggests that food literacy interventions are associated with improved food security (4). Traditionally food literacy interventions take a recipe-based approach to culinary nutrition and lack information about key components of food literacy, such as food storage and food waste reduction techniques. However, recent research by the PI contends that recipes may be difficult for food insecure individuals to implement at home, given the challenge of procuring ingredients (5), suggesting the need for a new approach. In addition, food insecure households face additional environmental challenges, such as owning fewer cooking utensils, compared to food secure households (6). Based on the Social Cognitive Theory, the Nourish intervention addresses these

limitations by incorporating food waste reduction, food storage knowledge, and improv cooking skills (cooking with what you have on hand) into food literacy and culinary nutrition education, as well as providing key cooking utensils. Eventually, our team plans to test the impact of the Nourish intervention on food literacy, perceived stress, diet quality and food security to determine if food literacy interventions can positively impact perceived stress, diet, and food security. The present pilot study will test the feasibility and acceptability of the Nourish intervention and corresponding evaluation, as well as provide participant feedback on the intervention.

*Please add relevant references at the end of the protocol, not at the end of this section.*

## 4.0 Inclusion and Exclusion Criteria

### Directions: Describe how individuals will be screened for eligibility.

Individuals will be verbally screened for eligibility to determine they are 18 years of age or older and determine that they are able to attend in-person, Nourish classes.

**Using the tables below, describe the inclusion and exclusion criteria that will define who will be included and excluded in your final study sample.**

Inclusion	
1.	Age range: Adults aged 18 and over
2.	Ability to attend classes (in person)
3.	
4.	

Exclusion	
1.	Non-English speaking
2.	
3.	
4.	

## 5.0 Number of Research Participants

**What is the target enrollment number of research participants? Make sure to include a specific upper limit. NOTE: If this is a multi-site study, also include the total number of research participants across all sites.**

**E.g., "We will enroll 25 subjects at CWRU and plan to enroll 150 subjects study wide."**

The target sample for Nourish is 40 participants. Twenty participants will receive the intervention immediately. An additional 20 participants will be in the delayed intervention control group. The upper limit is also 40 due to space constraints and small-group educational activities. This is not a multi-site study.

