## 8.0 Recruitment Methods

*Note: Attach all applicable recruitment materials to the last section of the Smart form under "Recruitment Materials."*

1. Which of the following methods will be used to recruit research participants? – *Select all that apply*
  - Email
  - Phone call
  - Letter
  - Advertisement (e.g., poster, flyer, etc.)
    - I attest that advertisements will only be placed with permission
  - Social media
    - Indicate the platform(s): *Click here to enter text.*
    - I attest that recruitment information will only be posted with permission
  - Other. *Please specify:* Snowball sampling
2. Describe when, where, how and by whom potential research participants will be recruited. Individuals involved in recruitment should be identified by role and not by name (e.g. study coordinator, co-investigator, research assistant).  
 The study coordinator will recruit participants upon IRB approval. We will primarily use flyers distributed at local community organizations, churches, food pantries, health clinics, and nonprofits. Participation in the Nourish intervention will make individuals eligible for an additional optional opportunity to establish a co-designed Nourish curriculum and structure. All 40 participants will be eligible for the second opportunity, as long as they complete at least 7/8 classes of the intervention. These participants will be invited with a recruitment letter provided at the conclusion of class 7 and class 8 of the intervention. The recruitment letter will be provided by a research assistant.
3. Describe the feasibility of recruiting the required number of suitable research participants within the agreed recruitment period. For example, how many potential research participants do you have access to?  
 As eligibility is broad enough to include a large portion of community members, we anticipate that it will be feasible to recruit 40 research participants. By recruiting at community organizations and locations near the setting of the intervention (teaching kitchen), it is more likely that these individuals will be able to attend in person classes at the kitchen, as well. We anticipate that this criteria will be the most challenging for individuals to meet, so will recruit near the physical meeting places used during the study.

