## 17.0 Data Analysis Plan

**Directions: Describe the data analysis plan, including any statistical procedures. If applicable, provide a power analysis, and study/safety endpoints.** Descriptive statistics of Likert scale weekly class survey questions and thematic analyses of weekly survey open-ended questions and focus groups will be used to assess participant perspectives of the pilot study. Classroom observation notes will be used to determine whether the Nourish and intervention is delivered as intended. Feasibility of recruitment and retention will be based on the number of participants recruited and retained through to completion of post-intervention assessments. In addition, we will analyze the pilot data collected. A series of one-way analysis of covariance will be conducted to determine statistically significant differences at post-intervention between the intervention and delayed intervention control groups on each outcome variable, controlling for the pre-treatment assessment scores on the variable analyzed. Outcome variables consist of total volume of food waste, FLEW assessment scores, food security, perceived stress, and diet quality as assessed by the Dietary Inflammatory Index.

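### Recruitment feasibility is measured only by a count that cannot exceed its target of 40, so a filled sample would not show yield, reasons for loss or time to fill

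*Combined protocol and SAP*

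**What the plan says.** Section 2.0 makes this a specific aim: "Determine the feasibility of the recruitment, retention, evaluation, and participant engagement methods".

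Section 17.0 gives one sentence of analysis for the recruitment and retention parts of that aim: "Feasibility of recruitment and retention will be based on the number of participants recruited and retained through to completion of post-intervention assessments". It names no number screened or approached, no unit of time and no breakdown of losses.

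Section 5.0 fixes the size: "The target sample for Nourish is 40 participants", made up of 20 immediate and 20 delayed participants. It then adds: "The upper limit is also 40 due to space constraints and small-group educational activities".

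Section 4.0 has people screened verbally for age and ability to attend in person, and excludes those who do not speak English. Section 8.0 relies mainly on flyers at community organisations, with snowball sampling as a further method. It states that "we anticipate that it will be feasible to recruit 40 research participants" and says of in-person attendance: "We anticipate that this criteria will be the most challenging for individuals to meet". The form asks there how many potential participants are accessible and about the recruitment period. The answer gives neither a number nor a length of time, and the optional timeline in Section 13.0 has no entry.

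**The concern.** Target and ceiling are the same number, so the recruitment measure stops rising at the point where the plan would be satisfied. Filling the sample is what the protocol expects, and it is the outcome on which the count says least. Forty people found quickly among a few enquirers and forty found slowly among many would be reported identically.

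The protocol also predicts where people will be lost, at the in-person requirement, but the stated measure does not count them. Whether that prediction is right, and by how much, is a useful thing for a pilot of recruitment methods to learn. Numbers screened, reasons and dates cannot be reliably reconstructed after recruitment closes. If they are not part of the plan, a full sample could leave the recruitment part of the second aim largely unanswered.

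**Working it through.** **Inputs from the documents.** Target 40 and upper limit 40 (Section 5.0); 20 immediate plus 20 delayed (Section 5.0); recruitment measure = number recruited (Section 17.0). No number screened, number accessible or recruitment period is given, so every such value below is an assumption shown as a range.

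**Step 1: the plan's own figure.** 20 + 20 = 40, which agrees with the stated target. No power, effect size or dropout rate is given, so 40 has no further derivation to reproduce.

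**Step 2: what the capped count can and cannot separate.** Let the supply of willing, eligible people, had there been no cap, be Poisson with mean μ (assumed). The recorded count reads 40 with probability

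P(Poisson(μ) ≥ 40) = 1 − Σ(k = 0 to 39) e^(−μ) μ^k / k!

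| Assumed μ | P(count reads 40) |
|---|---|
| 30 | 0.05 |
| 35 | 0.22 |
| 40 | 0.52 |
| 45 | 0.79 |
| 60 | 0.997 |
| 80 | about 1.00 |
| 120 | about 1.00 |

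Below the cap the count is informative: a supply of 30 would nearly always show as a shortfall. Above it the count is almost constant: supplies of 60 and 120 give the same record.

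**Step 3: yield behind a full sample.** Yield = consented / screened, with the Wilson interval

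[p + z²/(2n) ± z √(p(1 − p)/n + z²/(4n²))] / (1 + z²/n), z = 1.96.

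| Assumed number screened | Yield | 95% CI |
|---|---|---|
| 50 | 40/50 = 80% | 67–89% |
| 80 | 40/80 = 50% | 39–61% |
| 160 | 40/160 = 25% | 19–32% |

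The intervals do not overlap, so a screening denominator would tell these situations apart even at 40 recruited. The count reads 40 in each row.

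**Step 4: pace behind a full sample.** Pace = 40 / weeks. Assumed periods of 2, 8, 26 and 52 weeks give 20, 5, 1.5 and 0.8 per week. All participants attend baseline in week 1 of the study (Section 12.0), so recruitment must end by then, but its length is not stated and is not an outcome.

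**Step 5: retention.** Here the denominator exists, namely those recruited, and Section 17.0 names the endpoint. It can be reported as a proportion at once. For example, an assumed 32 of 40 is 80%, Wilson 95% CI 65–90%.

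**The case against.** Several stronger readings are tempting, and the documents do not support them.

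- *The cap is a fault.* It is not. The form asks for an upper limit, and Section 5.0 justifies it by space and small-group teaching. The weakness is in the Section 17.0 measure.
- *The count is uninformative.* Only when the sample fills. Step 2 shows that it does separate adequate from inadequate supply.
- *Any number could be declared feasible afterwards.* This is partly answered by the target of 40 and the expectation in Section 8.0 that 40 can be recruited. Calling 25 a success would sit badly with both. They are a stated expectation, though, and not a formal rule.
- *Retention has no denominator either.* It has one, and an endpoint. What is missing is a statement that it will be reported as a proportion with its uncertainty.
- *No screening log will be kept.* This cannot be shown. The list in Section 15.0 contains no screening counts, but the data collection tools are attachments that are not in the documents. What can be said is that Section 17.0 makes no use of screening data.
- *The pilot needs a go/amend/stop rule.* That is debatable. Redesign with participants is already planned, and Section 3.0 places the later test only at some future time. Illustrative bands such as 80% and above, 60–79% and below 60% would also separate poorly at this size: the interval for 32 of 40, 65–90%, covers most of the middle band as well as part of the upper one.

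The illustrative yields can also be challenged. Their spread, 160/50 = 3.2-fold, is the ratio of two assumed numbers and measures nothing about this trial. It shows only that the count cannot identify the yield.

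What stands is that, when the sample fills, the planned measure is silent on yield, reasons for loss and pace.

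**Conclusion.** The point holds in a limited form. Followed exactly, Section 17.0 would report a filled sample as 40 recruited and nothing more about recruitment. A shortfall would be visible; surplus, screening effort, losses at the in-person criterion and time to fill would not.

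The size of the gap in this trial cannot be estimated, because no number screened and no recruitment period is given. Under the assumptions shown, the same 40 is compatible with yields from 25% to 80% and with 0.8 to 20 recruits per week. The Poisson figures rest on an assumed supply and serve only to show where the count stops discriminating.

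This does not affect participant safety or the validity of the group comparison. It is a cheap improvement to the reporting of one stated aim, and it has to be made before recruitment starts.

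**What to change.** In Section 17.0, replace the sentence on recruitment and retention with a plan to report:

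- the numbers verbally screened, ineligible by reason (inability to attend in person listed separately), declined, and consented and randomised, by recruitment source and by week of recruitment. Flyers make the number approached hard to count, so the number screened is the practical denominator;
- consented divided by screened, with a 95% CI, and the number consented per week;
- retention as the proportion of those randomised who complete the post-intervention assessments, with a 95% CI.

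Sections 4.0 and 8.0 should say that this tally is kept.

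The cost is a short, de-identified tally kept by the study coordinator, who already recruits, and a few sentences of text. No extra participants or visits are needed. There are two downsides. The tally covers people before they consent, so it must be described in the IRB protocol. The result may also look less favourable than 40 of 40. A progression threshold may be added if the sponsor wants one, but it is not part of the required change.

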## 6.0 Special/Vulnerable Populations

*Check which of the following special populations you may include:*

- Adults unable to consent**
- Minors (infants, children, teenagers)**
  - Wards of the state (e.g. Foster Children)
- Pregnant Women** (only if targeted)
- Neonates**
- Neonates of Uncertain Viability**
- Employees**
- Prisoners**
- Illiterate Individuals**
- Non-English Speaking**
- Students**
- Data on a subjects' specific tribal nations**
- None**

1. If the research involves students or employees, describe how you will recruit so that:
  - a) Employers or educators do not know if someone participated (until after grades have been assigned in the case of educators)
  - b) Employers or educators do not *directly* recruit their own students or employees, and anything else to prevent feelings of coercion to those subordinate to their employer or educator.
 Not applicable.
2. If the research involves individuals that are included in a special/vulnerable population, describe the additional safeguards included to protect the rights and welfare of the individuals for each population indicated. Not applicable.
3. If excluding pregnant women, illiterate or non-English speaking individuals, provide a scientific rationale for the exclusion. Inconvenience or cost is not an acceptable rationale. Non-English speaking individuals will be excluded because we will be cooking in small groups during the intervention. While the risk of injury is no greater than that in everyday life activities, it is important that all participants be able to communicate with each other to maintain a safe cooking environment.

## 7.0 International information

- This is not an international study – *please leave rest of this section blank.*
- We will be conducting this research at the following international sites:  
 Click here to enter text.
- We are recruiting participants outside of the US from the following locations:  
 Click here to enter text.
- We are sending data outside of the US to the following locations:  
 Click here to enter text.

We are receiving data from outside of the US from the following locations:

*Click here to enter text.*

## 8.0 Recruitment Methods

*Note: Attach all applicable recruitment materials to the last section of the Smart form under "Recruitment Materials."*

1. Which of the following methods will be used to recruit research participants? – *Select all that apply*
  - Email
  - Phone call
  - Letter
  - Advertisement (e.g., poster, flyer, etc.)
    - I attest that advertisements will only be placed with permission
  - Social media
    - Indicate the platform(s): *Click here to enter text.*
    - I attest that recruitment information will only be posted with permission
  - Other. *Please specify:* Snowball sampling
2. Describe when, where, how and by whom potential research participants will be recruited. Individuals involved in recruitment should be identified by role and not by name (e.g. study coordinator, co-investigator, research assistant).  
 The study coordinator will recruit participants upon IRB approval. We will primarily use flyers distributed at local community organizations, churches, food pantries, health clinics, and nonprofits. Participation in the Nourish intervention will make individuals eligible for an additional optional opportunity to establish a co-designed Nourish curriculum and structure. All 40 participants will be eligible for the second opportunity, as long as they complete at least 7/8 classes of the intervention. These participants will be invited with a recruitment letter provided at the conclusion of class 7 and class 8 of the intervention. The recruitment letter will be provided by a research assistant.
3. Describe the feasibility of recruiting the required number of suitable research participants within the agreed recruitment period. For example, how many potential research participants do you have access to?  
 As eligibility is broad enough to include a large portion of community members, we anticipate that it will be feasible to recruit 40 research participants. By recruiting at community organizations and locations near the setting of the intervention (teaching kitchen), it is more likely that these individuals will be able to attend in person classes at the kitchen, as well. We anticipate that this criteria will be the most challenging for individuals to meet, so will recruit near the physical meeting places used during the study.

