## 12.0 Study Design/Procedures

### Directions:

- 1) **Describe the overall study design (e.g.: single visit, single-blind, double-blind, non-randomized, randomized, blood draw, investigational drug, device etc.).**
- 2) **Provide a description of all study-related research procedures being performed, including the length of time involved.**
- 3) **Include procedures being performed to monitor research participants for safety or minimize risks.**
- 4) **Describe the source records including medical or educational records, which will be used to collect data about subjects.**
- 5) **Include a description of any device being used to collect data (e.g., eye tracker, step counter). If the device itself is being studied, include additional information in Section 29.**

1. The study follows a randomized controlled trial with a delayed intervention control design. The immediate cooking class group will receive their intervention in week 3 of the study, and the delayed cooking class group will receive their intervention in week 13 of the study.

2. *Baseline assessment meeting:* Regardless of randomized group, all participants will attend this meeting in week 1. Participants will come to a branch of the Cleveland Public Library to sign their consent form and complete the survey portion of their baseline assessment, consisting of Percieved Stress Scale, USDA Food Security Screener, and the Food Literacy, Environment, and Waste (FLEW) assessment which will be conducted via Qualtrics on tablets provided by the researchers. Two aspects of the baseline evaluation will be conducted after the baseline meeting: a) a series of two 24-hour dietary recalls (via phone calls) lasting approximately 30 minutes each and b) participants will be asked to weigh and log their food waste for one week. During the baseline assessment meeting, participants will be asked to share their phone number and participants will be given a kitchen food scale and waste log. They will be asked to return the log on the first day of class. Additionally, participants will be told what they can expect to happen at each Nourish class and will be coached on how to sign up for GroupMe to receive out-of-class information about Nourish. The duration of the baseline assessment meeting will be

approximately 60 minutes, and will occur two weeks before the immediate cooking classes group's 8-week Nourish class sessions begin.

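### Nothing stops two adults from one household enrolling and being allocated to different arms, so a control may live with, and be partly treated by, an immediate-arm participant (minor; cheap to fix)

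*Combined protocol and SAP*

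**What the plan says.** - **Recruitment (Section 8.0).** The main route is flyers: "We will primarily use flyers distributed at local community organizations, churches, food pantries, health clinics, and nonprofits". Under the heading for other methods the plan enters "Snowball sampling", without saying what share of the sample it should supply.
- **Eligibility (Section 4.0).** Participants must be adults, able to come to the classes, and English-speaking. The verbal screen covers age and attendance. Household membership is neither asked about nor restricted.
- **Design and size (Sections 5.0 and 12.0).** "The study follows a randomized controlled trial with a delayed intervention control design". "The target sample for Nourish is 40 participants", which is also the ceiling. "Twenty participants will receive the intervention immediately", and another 20 wait. Both arms are counted in participants, but the unit and method of randomisation are not described.
- **Intervention and timing (Section 12.0).** After every class, participants take home groceries and a kitchen item. The immediate arm attends in weeks 3 to 10, the second assessment is in week 12, and the delayed arm attends in weeks 13 to 20.
- **Outcomes and analysis (Sections 12.0 and 17.0).** For the waste outcome, "participants will be asked to weigh and log their food waste for one week". Volume of food waste and food security are two of the five outcomes compared between arms by one-way ANCOVA on the baseline score. The model has no household term.
- **Background (Section 3.0).** The plan describes food insecurity partly as a household matter ("food insecure households face additional environmental challenges") and partly as something individuals experience.

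**The concern.** Two adults who share a home can both pass the screen and be allocated separately. If one is in the immediate arm and the other is a control, the control eats from the same groceries, uses the same equipment and sees the same cooking for eight weeks before the week 12 assessment. For outcomes tied to the kitchen, such as waste and food security, that control's result then carries part of the treatment effect, and the difference between arms shrinks.

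Co-enrolment is plausible, though the plan gives no rate for it. Section 26.0 offers each participant up to $125 + $125 + 8 × $5 = $290 in cash, plus about 8 × ($15 + $15) = $240 in groceries and equipment, so a second adult doubles what the home receives. Section 8.0 expects attendance in person to be the hardest criterion, and Section 25.0 leaves transport costs with participants; both favour people who can travel together. If household membership is never recorded, any contamination cannot be detected or adjusted for afterwards.

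**Working it through.** **The plan's own figure.** 20 + 20 = 40 agrees with the stated target. It rests on space and small-group teaching, not on a power calculation, so there is no power figure to reproduce.

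**Inputs.** From the documents: 20 per arm. Assumed: individuals are the unit of allocation; k pairs of co-residents enrol; a split pair makes its control member fully treated (contamination c = 1).

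**Chance that a pair is split.** Once one member is placed, 20 of the remaining 39 places are in the other arm: 20/39 = 0.513.

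**Expected dilution.** Each split pair affects 1 of 20 controls, so expected dilution is c × k × (20/39)/20 = c × k/39.

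| Co-enrolled pairs k | Expected split pairs | Expected dilution, c = 1 | Effect retained |
|---|---|---|---|
| 1 | 0.51 | 2.6% | 97% |
| 2 | 1.03 | 5.1% | 95% |
| 3 | 1.54 | 7.7% | 92% |
| 4 | 2.05 | 10.3% | 90% |
| 6 | 3.08 | 15.4% | 85% |

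At half contamination (c = 0.5) each dilution figure halves.

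**What this means for power (illustration only).** The plan states no alpha, effect size or SD. Assume two-sided alpha 0.05 and the difference that 20 per arm detects with 80% power: (1.96 + 0.842) × √(2/20) = 0.886 SD. Multiplying that difference by the retained fraction gives power of about 78%, 76%, 73%, 71% and 66% for k = 1, 2, 3, 4 and 6.

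**Does ignoring households make the standard error too small?** With 20 per arm and independent outcomes, the variance of the difference in means is 2σ²/20 = 40σ²/400. A same-arm pair with within-pair correlation ρ adds 2ρσ²/400; a split pair subtracts the same amount. Averaged over the allocation, the variance is multiplied by 1 + (2ρk/40) × (19/39 − 20/39) = 1 − ρk/780. At ρ = 1 and k = 6 this is 0.992, so there is no inflation on average. A simulation of 20:20 allocation with identical outcomes within pairs and a two-sample t-test at 5% (simpler than the planned ANCOVA) gave type I error of 0.050 to 0.051 for 1 to 6 pairs.

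Inflation appears only if one conditions on every pair falling in one arm. The design effect is then 1 + 2kρ/40, and at ρ = 1 the actual alpha is about 0.056, 0.062, 0.074 and 0.086 for k = 1, 2, 4 and 6. The chances of no pair being split are 49%, 24%, 6% and 1.4%.

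**The case against.** **The comparisons affected are secondary.** The three aims in Section 2.0 concern delivery, feasibility and participant views. Section 3.0 leaves impact testing to later work, and Section 17.0 adds the ANCOVAs after the feasibility measures. This stands, and it limits the severity. It does not remove the point: the plan still commits to significance tests between arms, and evaluation methods are part of what the pilot is meant to try out.

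**Several premises are inferred.** The unit of randomisation is not stated. Nor is it stated whether the waste log and the food security screener refer to the person or to the household. If they are strictly personal, contamination is weaker, though shared groceries and equipment still reach the control. Snowball referral is secondary to flyers, and flyers can also bring in two people from one home, so referral is one route to the problem and not the whole of it.

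**Stronger readings that do not hold.**
- A reader might infer that same-arm pairs count one household twice and leave the ANCOVA standard error too small. Under individual randomisation, same-arm and split pairs offset, and type I error stays near 5%.
- A reader might take three household pairs to mean 15% dilution. That needs three split pairs, or about six co-enrolled pairs in expectation, which is 12 of 40 participants. With three enrolled pairs the chance that all split is 13.5%, and expected dilution is 7.7%.
- A reader might assume that referrals will mostly be spouses or housemates. Nothing in the documents says so.

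**Conclusion.** The gap is real: the eligibility rules allow a control to live in a treated household during the whole comparison period, and no later step would reveal it. The consequence is a modest bias toward no difference in the food waste and food security comparisons, about 2.6% of the effect in expectation per co-enrolled pair. That figure assumes individual 20:20 allocation and full contamination, so it is an upper value for each pair; the number of pairs is unknown. The documents do not support a claim of invalid standard errors or of large dilution. Minor severity: a cheap improvement, worth making because it has to be in place before enrolment.

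**What to change.** In Section 4.0, add a question to the verbal screen on whether anyone in the same household has enrolled or plans to, and add the rule that one adult per household may enrol as a study participant. In Section 8.0, ask that snowball referrals come from outside the referrer's household. The rule covers people who arrive through flyers as well, and it brings the number of split pairs to zero.

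The cost is one question at screening. A few willing household members will not be enrolled, and recruitment may be slightly slower, which should be noted when recruitment feasibility is reported. N stays at 40, and no visit, instrument or analysis changes. It would also help to state the unit of randomisation and whether the waste log and food security screener are answered for the person or the household.
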